**NOTES:**

- T = Table, F = Figure, L = Listing, Y = Yes display generated.
- Stats Analysis = Represents TF related to any formal statistical analyses (i.e. modelling) conducted.
- Summary = Represents TF related to any summaries (i.e. descriptive statistics) of the observed raw data.
- Individual = Represents FL related to any displays of individual participant observed raw data.

### 7.3.1. Endpoints / Variables

As specified in the protocol, other efficacy endpoints/variables to be assessed in an exploratory manner are:

- Change from baseline in morning (AM) pre-dose Peak Expiratory Flow (PEF)
- Change from baseline in evening (PM) PEF
- Change from baseline in daily home trough FEV1
- Change from baseline in daily rescue medications use
- Change from baseline in SGRQ total score
- Percent of patients meeting a responder threshold of  $\geq 4$  points improvement (decrease) from baseline for the SGRQ total score
- Change from baseline in SGRQ domain scores
- Change from baseline in AQLQ total score
- Percent of patients meeting a responder threshold of  $\geq 0.5$  points improvement from baseline in AQLQ total score

- Change from baseline in E-RS total score
- Change from baseline in ACQ-5 total score
- Percent of patients meeting a responder threshold of  $\geq 0.5$  in change from baseline for the ACQ-5
- Annualized rate of moderate/severe exacerbations

In addition, the following endpoints (which were not specified in the protocol) will also be assessed in an exploratory manner:

- Change from baseline in daily home PM FEV1
- Annualized rate of severe exacerbations
- Time to first moderate/severe exacerbation
- Time to first severe exacerbation

### 7.3.2. Summary Measure

For the following endpoints, the mean change from baseline at 4-weekly intervals over the 24-Week post-baseline period and the mean over the 24-Week post-baseline period will be compared between treatment groups:

- Change from baseline in morning (AM) pre-dose Peak Expiratory Flow (PEF)
- Change from baseline in evening (PM) PEF
- Change from baseline in daily home trough FEV1
- Change from baseline in daily home PM FEV1
- Change from baseline in daily rescue medications use
- Change from baseline in E-RS total score
- 

For the following endpoints, the mean change from baseline at Week 24 will be compared between treatment groups:

- Change from baseline in SGRQ total score
- Change from baseline in SGRQ domain scores
- Change from baseline in AQLQ total score
- Change from baseline in ACQ-5 total score

For the following endpoints, the proportion of responders at Week 24 will be compared between treatment groups:

- Percent of patients meeting a responder threshold of  $\geq 4$  points improvement (decrease) from baseline for the SGRQ total score
- Percent of patients meeting a responder threshold of  $\geq 0.5$  points improvement (increase) from baseline in AQLQ total score
- Percent of patients meeting a responder threshold of  $\geq 0.5$  in change (decrease) from baseline for the ACQ-5

For the following endpoints, the ratio of exacerbation rates will be used to compare the treatments:

- Annualized rate of moderate/severe exacerbations
- Annualized rate of severe exacerbations

For the following endpoints, the average hazard ratio over the post-baseline period will be used to compare the treatments:

- Time to first moderate/severe exacerbation
- Time to first severe exacerbation

### **7.3.3. Population of Interest**

The exploratory efficacy analyses will be based on the ITT population.

### **7.3.4. Strategy for Intercurrent (Post-Randomization) Events**

A “treatment policy” strategy will be used to handle all intercurrent events, including treatment discontinuation, use of rescue medication and temporary treatment switches.

Participants who discontinue treatment prematurely are encouraged to return for all clinic visits as planned. Data collected post treatment discontinuation will be included in all analyses, as well as data collected after rescue medication or treatment switches.

This analysis corresponds to the “de facto” analysis.

For responder analyses, a composite strategy will be used to handle the intercurrent event of premature withdrawal from study. The endpoint analyzed will therefore essentially be the percent of participants who do not prematurely discontinue from the study and meet the responder threshold. This is the equivalent to handling participants with missing data as non-responders (see Section 10.7.2).

### **7.3.5. Statistical Analyses / Methods**

Details of the planned displays are provided in [Appendix 9: List of Data Displays](#) and will be based on GSK data standards and statistical principles.

Unless otherwise specified, endpoints / variables defined in Section 7.2.1 will be summarized using descriptive statistics, graphically presented (where appropriate) and listed.

Data collected on global assessment of severity and response to treatment, the supplemental asthma items on wheeze and short of breath, data on night time awakenings and data on asthma symptoms and physical activity, along with data collected for 11-item E-RS, will be evaluated to support qualification of the E-RS as an endpoint for asthma. These exploratory analyses will be the participant of a separate RAP. E-RS and the global assessment of severity and response to treatment will also be summarized in the CSR.

### 7.3.5.1. Statistical Methodology Specification

Endpoint / Variables

 
Change from baseline in morning (AM) pre-dose Peak Expiratory Flow (PEF)
 
Change from baseline in evening (PM) PEF
 
Change from baseline in daily home trough FEV1
 
Change from baseline in daily home PM FEV1
 
Change from baseline in daily rescue medications use
 
Change from baseline in SGRQ total score
 
Change from baseline in SGRQ domain scores
 
Change from baseline in AQLQ total score
 
Change from baseline in E-RS total score
 
Change from baseline in ACQ-5 total score
 

Model Specification

 
All analyses are based on the treatment policy (de facto) type estimand. Analyses are based on the ITT population.
 
Both on- and post-treatment data collected during the study will be included in the displays.
 
Baseline definitions are provided in Section 5.2
 
 
Diary data (Home Trough FEV1, PM FEV1, AM PEF, PM PEF, daily rescue medications use and E-RS)
 
 
For each given endpoint based on diary data, the summary data will be provided over 4-week incremental periods. Details on derivations for the diary data can be found in Section 10.6.3.
 
These endpoints will be summarized at baseline, over 4-week incremental periods and over Weeks 1-24, see Section 5.3.2.
 
The changes from baseline over 4-weekly periods of the 24-week treatment period will be analyzed using a MMRM model, adjusting for treatment, age, sex, region, baseline value, period, treatment by period interaction, and baseline value by period interaction. The average treatment effect over the 24-week period will also be obtained from the model.
 
Weekly mean change from baseline in trough FEV1 over the first 8 weeks of the treatment period will also be analyzed using a repeated measures model. Week will be added to the model as a covariate, in addition to treatment group, age (years), sex, region, baseline home trough FEV1. The model will also contain a week-by-treatment interaction term, and a week-by-baseline interaction term.
 
Additionally, weekly mean absolute and changes from baseline in AM PEF, PM PEF and home trough FEV1 will be summarized descriptively from Week 1 to 24.
 
 
Terms in the MMRM model - longitudinal analysis of mean change from baseline over 4-week incremental periods of the 24-weeks treatment period:
 
 
For each given parameter, the dependent variable is the period change from baseline
 
Period: Weeks 1-4, Weeks 5-8, Weeks 9-12, Weeks 13-16, Weeks 17-20, Weeks 21-24.
 
Covariates: 
 
Categorical: treatment group, sex, region and period.
 
Continuous: age, baseline value
 
 
 
Interaction: baseline*period, treatment*period
 
Repeated: period
 
The model will be fitted with an unstructured variance-covariance matrix.
 
The OM option in SAS will be used to derive the LS means based on the distribution of
 


the covariates observed in the data

Terms in the MMRM model - longitudinal analysis of weekly mean change from baseline over the first 8 weeks of the treatment period:

- Dependent Variable: period change from baseline in home trough FEV1
- Period: Week 1, Week 2, Week 3, up to and including Week 8.
- Covariates:
  - Categorical: treatment group, sex, region and period.
  - Continuous: age, baseline value
- Interaction: baseline\*period, treatment\*period
- Repeated: period
- The model will be fitted with an unstructured variance-covariance matrix.
- The OM option in SAS will be used to derive the LS means based on the distribution of the covariates observed in the data

#### PROs (SGRQ, AQLQ and ACQ-5)

- PRO data (both on- and post-treatment) collected at baseline, Week 4, 12 and Week 24 will be included in the analysis. Data will be summarized by treatment group and by visit.
- For SGRQ, the total score and the individual domain scores will be analyzed.
- Change from baseline will be analyzed using a mixed model repeated measures (MMRM) analysis, adjusting for covariates appropriately.

Terms in the MMRM:

- For each parameter, the dependent variable is the change from baseline
- Covariates:
  - Categorical: treatment group, sex, region, visit.
  - Continuous: age, baseline value
  - Interaction: baseline\*Visit, treatment\*Visit
- Repeated: Visit
- The model will be fitted with an unstructured variance-covariance matrix.
- The OM option in SAS will be used to derive the LS means based on the distribution of the covariates observed in the data

For Diary data and PROs, two models will be fitted; one with a response variable of change from baseline and one with the response variable as the raw value.

#### Model Checking & Diagnostics

- The Kenward and Roger method for approximating the denominator degrees of freedom and correcting for bias in the estimated variance-covariance of the fixed effects will be used.
  - In the event that a model fails to run using the KR method, then the residual method will be used instead for that endpoint.
- An unstructured covariance structure for the R matrix will be used by specifying 'type=UN' on the REPEATED line.
  - In the event that a model fails to converge, alternative correlation structures may be considered for the analysis of the endpoint.
  - Akaike's Information Criteria (AIC) will be used to assist with the selection of covariance structure.
- Distributional assumptions underlying the model used for analysis will be examined by obtaining a normal probability plot of the residuals and a plot of the residuals versus the fitted values (i.e. checking the normality assumption and constant variance assumption of the model respectively) to gain confidence that the model assumptions are reasonable.
  - If there are any departures from the distributional assumptions, alternative models will be explored using appropriate transformed data or non-parametric

methods if appropriate.
Model Results Presentation

• Least-Squares (LS) means and LS mean change from baseline values for each treatment group will be presented with their associated standard errors. The estimated treatment difference along with corresponding standard error, 95% CI and unadjusted p-value will be presented for all treatment comparisons specified in Section 2.4 at each timepoint.

• The LS mean change from baseline and treatment differences (and associated 95% CIs) at each timepoint will also be presented graphically.

• The weekly descriptive mean AM PEF, PM PEF and home trough FEV1 change from baseline over time will be plotted.

• A forest plot will display the treatment estimate and 95% CI for the SGRQ total score and domain scores at Week 24.

Endpoint / Variables

 
Percent of patients meeting a responder threshold of <math>\geq 4</math> points improvement (decrease) from baseline for the SGRQ total score
 
Percent of patients meeting a responder threshold of <math>\geq 0.5</math> points improvement (increase) from baseline in AQLQ total score
 
Percent of patients meeting a responder threshold of <math>\geq 0.5</math> in change (decrease) from baseline for the ACQ-5
 

Model Specification

 
The analysis is based on the de-facto estimand and is based on the ITT population.
 
Percent of participants meeting the responder threshold will be summarized by visit, and analyzed using a generalized linear model that is applicable to binary outcome measures, adjusted for covariates appropriately.
 
Computation of confidence intervals for the odds ratios is based on the individual Wald tests.
 
 
Terms in the GLMM:
 
 
Dependent Variable: Responder (Yes/No)
 
Covariates: 
 
Categorical: treatment group, sex, region and visit.
 
Continuous: age, Baseline value
 
 
 
Interaction: Baseline*Visit, treatment*Visit
 
Link function: Logit
 
The model will be fitted with an unstructured variance-covariance matrix.
 
The OM option in SAS will be used.
 

Model Checking & Diagnostics

 
The Kenward and Roger method for approximating the denominator degrees of freedom and correcting for bias in the estimated variance-covariance of the fixed effects will be used. 
 
In the event the model fails to run using the KR method, then the residual method will be used instead.
 
 
 
Pearson residuals will be plotted by using PLOTS=PEARSONPANEL option for the model statement in SAS.
 

Model Results Presentation

 
Number and percentage of responders and non-responders for each treatment at each Week will be presented. The number of non-responders due to missing data will also be presented.
 
The odds ratio for all treatment comparisons with associated 95% CI and p-value will be presented by visit.
 
A bar chart displaying the percentage of responders by treatment group will be presented.
 
Additionally, a shift table for ACQ-5 change from baseline to Week 24 in control categories will be produced (see Section 10.6.3).
 

Endpoint / Variables

 
Annualized rate of moderate/severe exacerbations
 
Annualized rate of severe exacerbations
 

Model Specification

 
Asthma exacerbations will be summarized, including number of participants with exacerbations, number of exacerbations and characteristics of exacerbations.
 
Analysis will be performed using a generalized linear model assuming a negative binomial distribution
 
The analysis is based on the treatment policy (de facto) type estimand, including all moderate/severe or severe (respectively) exacerbations observed during the study (both on- and post-treatment), based on the ITT population.
 

**Terms in the model:**

- Dependent variable: number of recorded (not imputed) exacerbations experienced per participant during the study (both on- and post-treatment).
- Covariates:
  - Categorical: treatment group, region, sex and severe asthma exacerbations in the previous year (0,  $\geq 1$ ).
  - Continuous: age.
- Offset: logarithm of time (year) on study
- The OM option in SAS will be used.
- Severe asthma exacerbations in the previous year is defined as the number of exacerbations that required either oral/systemic corticosteroids and/or antibiotics (not involving hospitalization) or those that required hospitalization as reported by participants at Visit 1.

**Model Checking & Diagnostics**

- The fit of the regression models will be examined using “Q-Q” plots of the standardized residuals. Interpretation of these plots will be aided by the addition of simulated envelopes as proposed by Atkinson (Atkinson, 1985).
- If the analysis fails to converge the covariate for severe asthma exacerbations in the previous year will be removed. If the analysis still fails to converge only summaries will be provided.

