## 2.3. Study Design

Overview of Study Design and Key Features	
205832 Study – UMEC (62.5 mcg) vs UMEC (31.25 mcg) vs Placebo 	

N=384 randomised
 
Population: Asthma
 
Open label ICS FF 100 mcg
	

Study population (Asthma)
 
Not well controlled Asthma ACQ 6 threshold >0.75 prior to randomization at Visit 2
	
Endpoints
 
Primary: Mean change from baseline in clinic trough FEV1 at week 24. Secondary: Mean change from baseline in clinic FEV1 at 3 hours post dose at week 24.

Design Features
	
 
This is a phase IIb, randomized, double-blind, 3-arm parallel group study, comparing the efficacy, safety and tolerability of UMEC (62.5 mcg and 31.25 mcg) administered once-daily in participants with asthma that is not well controlled (i.e. participants with an ACQ-6 total score >0.75 at Visit 2 [the Randomization Visit] despite treatment with maintenance ICS).
 
The target total number of randomized participants is approximately 384, with 128 participants randomized to each of the 3 double-blind treatment arms. All participants will be on a background therapy of FF 100mcg administered daily.
 
Participants who permanently discontinue study treatment are not required to withdraw from the study. Participants who have permanently discontinued study treatment and have not withdrawn consent are encouraged to continue in the study and complete all remaining protocol specified clinic visits.
 

Dosing
	
 
The double-blind treatment will be delivered via an ELLIPTA DPI once daily in the morning during the study treatment period. The open-label FF 100mcg will be delivered via an ELLIPTA DPI once daily following the double-blind treatment.
 
The duration of the treatment period is 24 weeks.
 

Overview of Study Design and Key Features	
Time & Events	
 
Refer to Appendix 2: Schedule of Activities
 

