**Model Results Presentation**

- Treatment group mean annual exacerbation rates, treatment rate ratios and associated 95% confidence intervals (CI) and p-values will be presented. The treatment rate ratios and associated 95% CIs will also be presented graphically.
- Percentage reduction in annual exacerbation rates and associated 95% CIs will also be presented.

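### The non-convergence rule for the exacerbation-rate models can discard an estimable rate ratio; Poisson regression with robust errors should be the first fallback

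*SAP*

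**What the plan says.** Section 7.3.5.1 gives one model for the annualized rates of moderate/severe and of severe exacerbations: "Analysis will be performed using a generalized linear model assuming a negative binomial distribution". The categorical terms are "treatment group, region, sex and severe asthma exacerbations in the previous year"; age is continuous. The time term is "Offset: logarithm of time (year) on study".

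The rule for numerical failure has two steps. First: "If the analysis fails to converge the covariate for severe asthma exacerbations in the previous year will be removed". Then: "If the analysis still fails to converge only summaries will be provided". The rule does not ask for the cause, does not mention a dispersion estimate at zero, and names no other count model or variance estimator.

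The output that hangs on the fit is: "Treatment group mean annual exacerbation rates, treatment rate ratios and associated 95% confidence intervals (CI) and p-values will be presented". Tables 2.52 and 2.54 and Figures 2.60 and 2.62 in Appendix 9 depend on it.

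**The concern.** The negative binomial model adds a dispersion parameter to the Poisson model. When events are few, the counts often show no extra-Poisson variation. The dispersion estimate then runs to its lower limit of zero, where some fitting routines report failure. The history covariate is not the source of that problem. Removing it leaves slightly more unexplained variation and takes out the only exacerbation-specific predictor, while region, sex and age stay. If the fit still fails, the rate ratio and its confidence interval are dropped, although a Poisson model could supply them.

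The rule is also out of line with the rest of Section 7.3.5.1. When a repeated-measures model fails, the plan considers another correlation structure. When the exact method for ties in the Cox model will not run, it switches to Efron. Both keep the treatment comparison. The Cox models also keep the history covariate, so after the first step the rate and time-to-event analyses would be adjusted differently.

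**Working it through.** The SAP gives no exacerbation rate, dispersion or history prevalence, so there is no stated figure to reproduce. The check uses the SAP's size and follow-up with assumed rates.

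**Inputs from the SAP.** Randomized by region (Section 5.4): Russia 174, USA 69, Rest of World 21 + 114 + 58 = 193; total 436. Allocation is 1:1:1 (Section 2.3). Follow-up: "The duration of the treatment period is 24 weeks", so 168/365.25 = 0.46 year, and 436 × 0.46 ≈ 200 person-years.

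**Assumptions.** Rates of 0.1, 0.2, 0.4 and 0.8 per year; negative binomial dispersion k = 0, 0.5, 1 and 2; 10% early withdrawal; 40% with a previous-year event, carrying a rate ratio of 2. There were 1,000 simulated trials per scenario.

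**Step 1: when the dispersion estimate is zero.** At the Poisson fit, the slope of the negative binomial log-likelihood in k at k = 0 is ½ Σ[(y − μ)² − y]. If it is not positive, the estimate is taken to be zero.

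*Illustration with an intercept only and 20 events in 436 participants.* The sum is Σy² − 20²/436 − 20 = Σy² − 20.92.
- Twenty participants with one event each: Σy² = 20, sum = −0.92, estimate zero.
- Eighteen with one event and one with two: Σy² = 22, sum = +1.08, estimate above zero.

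So at this event count the answer can turn on one participant's second event. A binary history covariate moves it little.

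**Step 2: how often the estimate is zero, and whether removing the covariate changes that.**

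| Assumed rate per year | Expected events (full follow-up) | Estimate at zero, over the k values | Still at zero without the covariate (k up to 1) |
|---|---|---|---|
| 0.1 | 20 | 35–65% | 91–94% |
| 0.2 | 40 | 8–67% | 75–87% |
| 0.4 | 80 | 0.3–65% | 58–78% |
| 0.8 | 160 | 0–3% if k ≥ 0.5 | – |

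With 30% history prevalence, rate 0.2 and k = 0.5, the share at zero fell from 42% to 35%, a net cure of 7/42 = 17%. A further set of fits at 0.1 to 0.4 per year left 67–97% of zero-dispersion datasets at zero.

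**Step 3: whether zero dispersion means failure to converge.** This depends on the routine.
- One maximum-likelihood routine (6 scenarios × 150 = 900 fits) failed in 411 of 411 zero-dispersion datasets and in 74 of the other 489. Zero dispersion made up 411/485 = 85% of its failures.
- In the further set of fits only part of the zero-dispersion datasets failed. Where failures were common, 88–100% of them were zero-dispersion datasets.
- A routine with dispersion bounded at zero or above (9 scenarios × 150 = 1,350 fits) converged in all 605 zero-dispersion datasets and in the other 745. In the zero-dispersion datasets its treatment log rate ratios lay within 0.053 of the Poisson values.

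None of these runs used SAS, the software named in Appendix 5.

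**Step 4: whether Poisson with robust errors would serve.** With all covariates kept, the nominal 95% interval for the treatment log rate ratio missed the true value in 2.6% to 6.9% of runs across the scenarios; at k = 2 the range was 4.6% to 6.2%. In the further set it was 1–9%, but with 120 runs each (Monte Carlo standard error √(0.05 × 0.95/120) = 2.0 points). With model-based Poisson errors it reached 15.3% at k = 2 and 0.8 per year, so the robust errors are needed. The only case without an estimable ratio was an arm with no events: at most 0.7% of runs at 0.1 per year, and none from 0.2 per year up.

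**The case against.** The strongest objection is that zero dispersion is not non-convergence. The rule acts only when the fit fails, and at zero dispersion the negative binomial likelihood is the Poisson likelihood, with finite coefficients and a usable ratio. A reader might infer from the table that a third or more of such trials would lose their rate ratio. The documents do not support that. Every event rate is assumed, and the share of zero-dispersion datasets that failed ran from all to none across the routines tried. This objection stands, and the table should not be read as a trigger frequency.

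A reader might also infer that exacerbations would be left without any treatment comparison. They would not: Section 7.3.5.1 plans Cox hazard ratios with confidence intervals and p-values for the same two event definitions. Both rates are exploratory, the multiplicity hierarchy in Section 5.6 covers only the primary endpoint, and the fallback is pre-specified, so it invites no post hoc choice. All of this stands and limits the importance.

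Sparse cells are another possible cause. Separation on a covariate occurred in 5–6% of datasets at 0.1 per year and in at most 0.5% from 0.2 per year up. Removing the history covariate is reasonable when it is the one separating, but the rule removes it whatever the cause.

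The moderate/severe endpoint includes moderate events and so has the higher rate. If that rate is near 0.8 per year with real overdispersion, the estimate would rarely be zero.

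**Conclusion.** The point holds in a limited form. The rule does not address a likely cause of failure in sparse counts, and it can end with no rate ratio when a valid one is estimable. The mechanism is supported at assumed rates of 0.1 to 0.4 per year, which makes severe exacerbations the more plausible case. There, removing the covariate left most zero-dispersion fits unchanged (58–97% across the assumption sets), while Poisson with robust errors stayed close to nominal coverage.

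The frequency cannot be stated, for want of event rates and of the fitting routine's behaviour at zero. What is at risk is the rate ratio for exploratory endpoints, not a primary conclusion and not the whole exacerbation comparison. It is worth changing because the change is cheap, and because an undefined trigger lets software behaviour decide whether a ratio is reported.

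**What to change.** Replace the two-step rule for the rate models in Section 7.3.5.1 with:

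> If the negative binomial model fails to converge, or its dispersion estimate is at zero, a Poisson regression with the same covariates and offset and robust (sandwich) standard errors will be used. Only if a treatment rate ratio is still not estimable (for example, no events in an arm) will summaries alone be provided.

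Keep both the history covariate and region in the model. Sections 2.1 and 5.5.1 added region deliberately, and nothing here argues for removing it. The summaries-only step stays as the last resort, because Poisson regression gives no finite ratio either when an arm has no events.

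The cost is two sentences and one contingent procedure. The downside is that robust errors can be slightly off nominal coverage when events are very few.
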